#### 4.1.2 Per-Protocol Analysis Set (Primary Analysis Set)

For per-protocol analysis, only subjects who had the test device implanted in the target vessel and had no major protocol deviations will be included in the analysis. Major protocol deviations are defined as protocol deviations with a level of seriousness such that inclusion of the subject(s) would unacceptably bias the primary endpoint analysis. An example of a major protocol deviation might be failure to satisfy eligibility criteria to a degree where the subject does not fit the underlying scientific model for the treatment.

The per-protocol set will be used for the primary analyses of the primary endpoint. Ideally this analysis set will consist of all subjects from the ITT set with technical success (test device implanted).

#### 4.2 Timing of Analyses

#### 4.2.1 Primary Endpoint Analysis

The primary endpoint analysis will occur when enrollment has been completed and primary endpoint status has been determined for all enrolled and implanted subjects (generally after the one-year follow-up has been completed).

#### 4.2.2 Staged Analysis

In accordance with the IDE approval letter from FDA dated December 13, 2012, the Gore SCAFFOLD Clinical Study was initially limited to enrollment of 100 subjects, with the following interim analysis requirement:

[figure not shown]
"Your IDE application has been approved as a staged study. You may request approval to expand enrollment in your study when you have submitted an IDE supplement which provides the 6-month results from the first 50 patients enrolled."

Thus, when the 6-month follow-up evaluation is completed (or final 6-month follow-up status determined) for the first 50 subjects enrolled, the data for these 50 subjects will be analyzed and results presented for safety and efficacy endpoints measured at procedure, 30 days and 6 months.

#### 4.3 **Primary Endpoint**

The primary endpoint of 1-year MAE will be calculated as a subject-based binomial proportion. The numerator will be the count of subjects who experience death, any stroke, or MI through 30 days post-index procedure, or ipsilateral stroke through one year (365 days) post-index procedure. The denominator will be the count of subjects free of MAE and with clinical follow-up of at least 335 days post-index procedure, plus the count of subjects in the numerator. Only MAE adjudicated by the CEC will be used in this analysis. Acceptable clinical follow-up includes the Subject Evaluation CRF, duplex ultrasound, modified Rankin scale, and NIHSS.

A one-sided 95.1% upper confidence bound will be calculated (using the standard error based on  $H_0$ ) and compared to the prespecified performance goal. If this bound is less than the performance goal, then the primary endpoint is met and the test device will have demonstrated acceptable performance. The *P* value for the corresponding one-sided normal

approximation to the binomial test will be reported. The primary hypothesis test will use  $\alpha$ =0.049 to ensure an overall Type-1 error rate  $\leq$ 0.05.

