5.14. Subject Study Completion

A subject has completed the study when he/she has completed the 3-year follow-up evaluations. Any subject that does not complete these requirements due to voluntary withdrawal, physician withdrawal, death, or any other reason will be considered as an early withdrawal. In the event of a Technical Failure (no GORE[®] Carotid Stent implanted), the subject will be followed through the 30-day visit and will be considered to have completed the study.

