9.1.4. Subject Death

If a subject dies while participating in the study, the cause of death will be reported as the adverse event and "death" reported as the event outcome on the AE case report form. If the subject has other ongoing adverse events at the time of death, the outcome status of those events should be reported as "resolved" on the AE case report form.

The Investigator should obtain all medical records including death certificate and autopsy report for inclusion in reporting to the Clinical Events Committee.

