#### 2.5 Study Endpoints

#### 2.5.1 Primary Endpoint

The primary study endpoint is a composite of Major Adverse Events (MAE) defined as death, any stroke, or myocardial infarction (MI) through 30 days post-index procedure, and ipsilateral stroke between 31 days and 1 year (365 days). All primary endpoint events will be adjudicated and determined by the study Clinical Events Committee (CEC).

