#### 3.4 Clinical Events Committee

An independent Clinical Events Committee (CEC) will review potential primary endpoint events and adjudicate events based on endpoint definitions in the study protocol. The CEC will be comprised of an interdisciplinary team with pertinent knowledge in carotid stenting or the cardiovascular and/or nervous system who are not directly involved in the conduct of the study. The members will be compensated for their involvement in the CEC, including reimbursement for reasonable travel expenses to attend meetings.

This committee will operate under prespecified procedures as outlined in the CEC Charter. The adjudication process will be initiated after a potential primary endpoint event is reported by the site.

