#### 4.5 Adverse Events

All site-reported AEs will be MedDRA coded and grouped by MedDRA System/Organ Class (SOC) and by MedDRA Preferred Term within SOC. AEs will also be grouped by seriousness (SAE vs. nonserious AE), primary relationship (stent, EPD, procedure, medication, disease, not related, and unknown) and timing of onset (procedure, pre- and post-discharge). AEs will be summarized as rates given by subject-based binomial proportions. The numerator will be the count of subjects who experienced one or more episodes of the AE of interest in the time period of interest. The denominator will be the count of subjects free of the AE of interest through the time period of interest and with sufficient clinical follow-up for the time period of interest, plus the count of subjects in the numerator. Unless otherwise specified for a particular endpoint measure, all enrolled subjects in the analysis set of interest will be considered evaluable and will contribute to the denominator.

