#### 4.10 Additional Analyses

Additional subgroup analyses may be performed based on variables identified to be significant predictors (p-value<0.05) in multivariate analyses.

Sensitivity analyses of the primary endpoint will be conducted and will include, at a minimum, a worst-case analysis (nonevaluable subjects considered failures) and, if necessary, a tipping point analysis (threshold of successes vs. failures at which the primary test conclusion changes).

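### The primary denominator drops MAE-free subjects who die after day 30 without 335 days of follow-up, and the worst-case analysis may then count those deaths as failures

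*SAP*

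**What the plan says.** SAP 2.5.1 defines the primary endpoint as death, any stroke or MI through day 30, and after that only "ipsilateral stroke between 31 days and 1 year (365 days". A death after day 30 is not itself an event.

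SAP 4.3 computes a binomial proportion. The numerator is every subject with an MAE. For the rest: "The denominator will be the count of subjects free of MAE and with clinical follow-up of at least 335 days post-index procedure". The follow-up it describes consists of visit assessments; no provision is made for a subject who dies.

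Four other places bear on the question:

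- SAP 4.2.1 times the analysis for when "primary endpoint status has been determined for all enrolled and implanted subjects", but does not say what status a late death has.
- SAP 4.5 gives a default: "Unless otherwise specified for a particular endpoint measure, all enrolled subjects in the analysis set of interest will be considered evaluable". For the primary endpoint, 4.3 does specify otherwise.
- Protocol 5.14 says a subject who does not finish "due to voluntary withdrawal, physician withdrawal, death, or any other reason will be considered as an early withdrawal".
- SAP 4.10 requires "a worst-case analysis (nonevaluable subjects considered failures" and, if necessary, a tipping point analysis. It does not define 'nonevaluable'. Protocol 10.4.6 requires both analyses.

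**The concern.** A subject who dies between day 31 and day 365 with no MAE can have no later event. The endpoint definition then settles the 1-year status as MAE-free. SAP 4.3 nevertheless treats that subject like one who left the study alive with stroke status unknown: both fall out of the denominator.

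Two things follow. Removing non-events raises the estimated MAE rate and reduces the number analysed. And if 'nonevaluable' in SAP 4.10 means outside the 4.3 denominator, the worst case fails subjects whose status is known together with subjects whose status is missing. The sensitivity analyses carry no success criterion, but a reader will use them to judge how much the missing data matter. Failing subjects who left alive with unknown status is proper in a worst case; failing confirmed MAE-free deaths is not.

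**Working it through.** **Step 1: trace one subject.** Death on day 200, no earlier MAE.

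- Numerator (SAP 4.3): no, because the death is after day 30 and there was no ipsilateral stroke.
- Denominator (SAP 4.3): no, because 200 < 335.

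The subject is in neither count. An MAE-free subject who dies after 335 days of follow-up stays in.

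**Step 2: inputs.**

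- From the documents: N = 312 (SAP 2.4); one-sided 95.1% bound with the standard error under H0 (SAP 4.3). The stated alpha reproduces as 1 − 0.951 = 0.049, giving z = 1.6546. The 335-day cut reproduces as 365 − 30, from the window in SAP 3.2.
- Not legible in the public text: the performance goal (PG), the expected rate and any attrition allowance. So 312 cannot be reproduced, and the check does not depend on it.
- Assumed: all 312 implanted and in the analysis set; 20 MAE; late MAE-free deaths / alive with unknown status of 6/6, 16/16 and 25/22; PG of 12, 15 and 18%.

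**Step 3: primary proportion.** As written, x/(312 − deaths − unknown). With deaths kept, x/(312 − unknown).

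| Deaths/unknown | As written | Deaths kept | Difference |
|---|---|---|---|
| 6/6 | 20/300 = 6.67% | 20/306 = 6.54% | 0.13 points |
| 16/16 | 20/280 = 7.14% | 20/296 = 6.76% | 0.39 points |
| 25/22 | 20/265 = 7.55% | 20/290 = 6.90% | 0.65 points |

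(Differences are taken before rounding.) The deaths-kept column treats every late death as confirmed MAE-free, so these differences are upper limits.

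Bound = x/n + 1.6546·√(PG(1 − PG)/n). The highest as-written bounds occur at n = 265: 10.85, 11.18 and 11.45% for PG of 12, 15 and 18%. All pass, so all nine cases pass under either rule.

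Largest passing MAE count, as written vs deaths kept:

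| PG | 6/6 | 16/16 | 25/22 |
|---|---|---|---|
| 12% | 26 vs 27 | 24 vs 26 | 23 vs 25 |
| 15% | 34 vs 35 | 32 vs 34 | 30 vs 33 |
| 18% | 42 vs 43 | 39 vs 42 | 37 vs 41 |

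The two rules disagree only in a band 1 to 4 subjects wide.

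**Step 4: direction.** For fixed x, both terms of the bound fall as n rises. A result that passes as written therefore also passes with MAE-free deaths kept. The written rule cannot add false successes.

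**Step 5: worst case.** All 312 are in the denominator. The margin 1.6546·√(PG(1 − PG)/312) is 3.04, 3.34 and 3.60 points, so the largest passing count is 27, 36 and 44 at PG of 12, 15 and 18%.

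- Deaths and unknowns failed: 32, 52 and 67 of 312 (10.3, 16.7, 21.5%).
- Unknowns only failed: 26, 36 and 42 of 312 (8.3, 11.5, 13.5%).

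Result with deaths failed / with unknowns only failed:

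| PG (limit) | 6/6 | 16/16 | 25/22 |
|---|---|---|---|
| 12% (27) | **miss / pass** | miss / miss | miss / miss |
| 15% (36) | pass / pass | **miss / pass** | miss / miss |
| 18% (44) | pass / pass | **miss / pass** | **miss / pass** |

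The result changes in 4 of 9 cells. These contrasts also assume that all late deaths are confirmed. Subtracting the unknowns-only count from the limit shows how many unconfirmed deaths each changed cell tolerates: 27 − 26 = 1; 36 − 36 = 0; 44 − 36 = 8; 44 − 42 = 2.

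**Step 6: tipping point.** From 20/312, the added failures needed are 28 − 20 = 8, 37 − 20 = 17 and 45 − 20 = 25. At 15% with 16/16, 17 can be reached among 32 'nonevaluable' subjects but not among the 16 with unknown status. That example turns on one subject.

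**The case against.** The strongest reply is that a late death is not automatically a known non-event. Visits fall at 30 days, 6 months and 1 year, so a death on day 330 can follow about 330 − 180 = 150 days without a scheduled assessment, and an unwitnessed death may itself be an ipsilateral stroke. This stands. It is why the figures are upper limits and why the fix requires confirmation by the CEC.

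Second, the written rule is conservative, and whether it is wrong for the comparison depends on how the performance goal was built. If the goal's source data used the same evaluable-subject denominator, keeping late deaths would create a mismatch in the device's favour. SAP 2.6 to 2.8 and Protocol 10.1 to 10.3 cannot be read here, so a matching convention, or an allowance within 312, cannot be excluded. This stands too, and it conditions the change to the primary denominator.

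Third, late deaths may be few, since Protocol 4.3 excludes life expectancy under one year. In the 6/6 case the primary shift is only 0.13 points. But the worst-case result still changes there at a 12% goal.

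Fourth, some of the remedy is already in place. Protocol 9.1.4 says: "The Investigator should obtain all medical records including death certificate and autopsy report for inclusion in reporting to the Clinical Events Committee". That is right. What remains open is that SAP 3.4 says "The adjudication process will be initiated after a potential primary endpoint event is reported by the site", and a death after day 30 is not by itself such an event.

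A reader might also infer that SAP 4.10 orders late deaths to be failed, or that Protocol 5.14 makes them nonevaluable. Neither is supported. The first is one reading of an undefined term. The second is an administrative category for not completing three years and says nothing about the endpoint.

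**Conclusion.** The point holds on the text. SAP 4.3 excludes subjects whose 1-year status can be known under SAP 2.5.1, and no readable passage restores them. A definition in the illegible sections cannot be ruled out.

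The effect on the primary estimate is small and against the device: at most about 0.1 to 0.7 points in the assumed examples. A reader might infer that the rule flatters the device or endangers the primary conclusion. It does neither: type I error is not inflated, and all nine primary results are unchanged.

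The practical weight lies in SAP 4.10. How 'nonevaluable' is read changes the worst-case result in 4 of 9 assumed combinations and leaves it unchanged in five. One of the four has no room for a single unconfirmed death. All event counts, death counts and goals are assumptions. This is worth settling before data are seen, but it does not threaten the trial's main inference.

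**What to change.** Before data are seen:

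1. **SAP 4.10.** Define 'nonevaluable' as primary endpoint status unknown, and apply the worst-case and tipping point analyses only to those subjects.
2. **SAP 4.3.** Count a subject who dies after day 30 without 335 days of follow-up as evaluable and MAE-free if the CEC, using the death records already collected under Protocol 9.1.4, confirms no MAE before or at death. Otherwise classify the status as unknown. Leave the 335-day rule for living subjects as it is.
3. **Reporting.** Give the primary result under both the current and the amended denominator. First check that the amended rule matches how the performance goal's source data treated late deaths. If it does not, keep the current rule as primary and report the amended one as a prespecified supplementary analysis.

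The cost is a few sentences in the SAP and limited CEC review of late deaths. No extra subjects or visits are needed, and the test formula is unchanged. The downside is a denominator change that slightly favours the device, which is why both results should be shown.

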#### 4.4 Secondary Endpoints

Secondary endpoints (subject-based unless otherwise specified) will be descriptive only; no formal statistical hypotheses will be tested. Secondary endpoints will be summarized at the specified time points using the descriptive statistics described above. No claims of statistical significance will be made based on secondary endpoint results. *P* values from these tests will not be reported in labeling, but may be used for scientific presentations and/or manuscripts.

**Stent Technical Success:** Successful deployment of the test device. It will be calculated as a subject-based binomial proportion. The numerator will be the count of subjects who experience successful deployment of the test device at the index procedure (based on the Procedure CRF). The denominator will be the count of subjects in whom implantation of the test device was attempted (based on the Procedure CRF).

**EPD (Embolic Protection Device) Technical Success:** EPD Technical success is defined as: GORE® Embolic Filter delivered, placed, and retrieved without requiring assisting interventional methods. It will be calculated as a subject-based binomial proportion. The numerator will be the count of subjects who experience successful use of the EPD during deployment of the test device at the index procedure (based on the Procedure CRF). The denominator will be the count of subjects in whom implantation of the test device was attempted (based on the Procedure CRF).

[figure not shown]
**Procedure Success:** Stent Technical Success, <30% residual angiographic stenosis by visual assessment post-procedure in the target lesion, and no in-hospital (pre-discharge) Major Adverse Event. It will be calculated as a subject-based binomial proportion. The numerator will be the count of subjects who experience Stent Technical Success and <30.0% "Post intervention lesion % residual stenosis" (from the Procedure CRF) and are free of any CEC-adjudicated in-hospital MAE. The denominator will be the count of subjects in whom implantation of the test device was attempted (based on the Procedure CRF).

**30-Day Major Adverse Events:** Composite of death, any stroke, or myocardial infarction through 30 days post-index procedure. It will be calculated as a subject-based binomial proportion. The numerator will be the count of subjects who experience CEC-adjudicated MAE through 30 days post-index procedure. The denominator will be the count of subjects free of MAE through 30 days post-index procedure and with clinical follow-up of at least 23 days post-index procedure, plus the count of subjects in the numerator.

**In-stent Restenosis:** Measured as percent stenosis at follow-up evaluation within the stented lesion or within 5 mm proximal or distal to the stent. Additionally will assess percent of subjects with stenosis  $\geq$ 50% by ultrasound and  $\geq$ 80% by angiographic evaluation.

The text above is taken verbatim from the clinical protocol. There are three separate endpoint measures implied by this description, defined below:

**In-stent Percent Diameter Stenosis:** calculated as a subject-based categorical frequency distribution of "In Stent Stenosis Category" as reported on the Carotid Artery Duplex Scan CRF among subjects with a valid, nonmissing value for this item.

The stenosis categories are the following:

- Patent
- 50-79%
- >70%
- 80-99%
- Occluded

**In-stent Restenosis By Ultrasound:** calculated as a subject-based binomial proportion. The numerator will be the count of subjects with stenosis ≥50% by ultrasound (indicated as any valid, nonmissing stenosis category other than "Patent") as reported on the Carotid Artery Duplex Scan CRF. The denominator will be the count of subjects with a valid, nonmissing value for this item.

**In-stent Restenosis By Angiography:** calculated as a subject-based binomial proportion. Restenosis failures will be indicated by an angiography core lab-adjudicated stenosis of ≥80% as reported on the Angio Core Lab Adjudication CRF. Not all subjects will have a follow-up angiography performed, only those whose ultrasound-determined stenosis and/or clinical symptoms provokes an angiography by the investigator. The denominator will be the count of subjects with a valid, nonmissing value for ultrasound-determined stenosis.

**Target Lesion Revascularization (TLR):** any clinically-driven revascularization procedure of the original treatment site, including angioplasty, stenting, endarterectomy, or thrombolysis, performed to open or increase the luminal diameter inside or within 5 mm of the previously treated lesion. This will be calculated using Kaplan-Meier (K-M) survival analysis. Events will be subjects who experience TLR as reported on the Reintervention CRF. Censored observations will be subjects free of TLR. K-M estimates corresponding to the study follow-up intervals will be reported, as well as a graph of the entire survival distribution.

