6.4. Core Labs

Core Lab services for this study will be provided by:

Please refer to the Imaging Guidelines for each specific core lab for instructions on submission of images and specific requirements for the images.

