#### 2.5.2 Secondary Endpoints

Stent Technical Success: Successful deployment of the test device.

**EPD (Embolic Protection Device) Technical Success:** Technical success for the GORE® Embolic Filter is defined as: EPD delivered, placed, and retrieved without requiring assisting interventional methods.

**Procedure Success:** Stent Technical Success, <30% residual angiographic stenosis by visual assessment post-procedure in the target lesion and no in-hospital (pre-discharge) Major Adverse Event.

**30-Day Major Adverse Events:** Composite of death, any stroke, or myocardial infarction through 30 days post-index procedure.

**In-stent Restenosis:** Measured as percent stenosis at follow-up evaluation within the stented lesion or within 5 mm proximal or distal to the stent. Additionally will assess percent of subjects with stenosis  $\geq$ 50% by ultrasound and  $\geq$ 80% by angiographic evaluation.

**Target Lesion Revascularization (TLR):** any clinically driven revascularization procedure of the original treatment site, including angioplasty, stenting, endarterectomy, or thrombolysis, performed to open or increase the luminal diameter inside or within 5 mm of the previously treated lesion.

[figure not shown]

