#### 6.2 Statistical Output Specifications

A specifications document, or "spec," is created for each statistical output (Table, Listing, or Figure) and contains, at a minimum:

- Title and footnote information
- Column headers
- General appearance of each cell (for tables and listings)
- If the spec includes a figure, either an example figure or a detailed description of the figure is included in this section
- Variables, procedures, and/or calculation logic used in the statistical output
- Change log section

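### SAP 4.4 in-stent restenosis: the duplex categories overlap above 70%, and the angiographic ≥80% rate counts a severe duplex without an angiogram as a non-failure

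*SAP*

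**What the plan says.** Protocol 3.2.3 and SAP 2.5.2 name the outcome in the same terms: "Additionally will assess percent of subjects with stenosis" of at least 50% by ultrasound and at least 80% by angiography. SAP 4.4 turns this into three measures.

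- **Duplex distribution.** One category per subject, taken from the In Stent Stenosis Category item, "as reported on the Carotid Artery Duplex Scan CRF among subjects with a valid, nonmissing value for this item". The printed categories are Patent, 50-79%, >70%, 80-99% and Occluded.
- **Ultrasound rate, ≥50%.** The numerator is "indicated as any valid, nonmissing stenosis category other than" Patent.
- **Angiographic rate, ≥80%.** On the numerator: "Restenosis failures will be indicated by an angiography core lab-adjudicated stenosis of" 80% or more. On who is imaged: "Not all subjects will have a follow-up angiography performed, only those whose ultrasound-determined stenosis and/or clinical symptoms provokes an angiography by the investigator". On the denominator: "The denominator will be the count of subjects with a valid, nonmissing value for ultrasound-determined stenosis".

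Protocol 5.11 requires a duplex of the target vessel at every follow-up visit. Protocol 5.2 schedules no follow-up angiogram; after the index procedure, angiography appears only as an unscheduled test when clinically indicated. SAP 4.4 also makes all secondary endpoints descriptive.

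**The concern.** There are two linked problems.

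First, the duplex categories are values of a single item but are not mutually exclusive. The >70% category has no upper limit, and neither document says when it is used instead of 50-79%, 80-99% or Occluded. An entry recorded as >70% cannot be placed above or below 80%, the threshold of the angiographic measure.

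Second, the angiographic numerator is open only to subjects who had an angiogram, while the denominator takes everyone with a valid duplex. In effect, no angiogram is read as below 80%. That is reasonable for a Patent duplex, but not for one reading 80-99% or Occluded.

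At stake is what the reported figure means. A low rate could reflect little severe restenosis, or few severe duplex results followed by an angiogram. The SAP does not ask for the cross-count of severe duplex results by angiogram status that would separate the two. The duplex table could serve as a check, but it is blurred at the threshold that matters. No hypothesis is tested on this endpoint, so the printed rate is the whole result.

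**Working it through.** The documents give no restenosis rate, count of severe duplex results, referral fraction or confirmation fraction, so there is no planned figure to reproduce. The check has two parts.

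**1. Category membership, from the list in SAP 4.4**

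| Stenosis | Categories that fit |
|---|---|
| 55%, 69% | 50-79% only |
| 71%, 75%, 79% | 50-79% and >70% |
| 80%, 85%, 99% | >70% and 80-99% |
| 100% | >70% and, read literally, Occluded |

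Every whole-percent value above 70% fits two categories. All the overlap comes from >70%; 50-79% and 80-99% meet but do not overlap. The ≥50% rate is unaffected because it counts every category other than Patent, wherever an entry sits among them.

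**2. Effect of the denominator rule**

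Let N be the subjects with a valid duplex, U those with duplex 80-99% or Occluded and no angiogram, and p the fraction of U that angiography would confirm at ≥80%. Let L be the subjects in other duplex categories without an angiogram, and q the fraction of them that would be ≥80% on angiography. Then

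understatement = (U × p + L × q) / N.

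The severe-duplex part, U × p / N, lies between 0 (every such subject referred) and U / N. The second term is not bounded by U / N.

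*Per subject.* With N assumed to be 280 (about 90% of the planned 312), 1/280 = 0.36 percentage points. For N = 300 it is 0.33, and for N = 250 it is 0.40.

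*Illustrative range, all inputs assumed.* Take 10 to 20 severe duplex results with 40% to 70% referred. U then runs from 10 × 0.3 = 3 to 20 × 0.6 = 12. With p from 0.3 to 1.0, the severe-duplex part runs from 3 × 0.3 / 280 = 0.3 points to 12 × 1.0 / 280 = 4.3 points.

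*Example with tighter lesions referred first (assumed).* Of 20 severe subjects, 10 are referred and 9 confirmed; 5 of the other 10 would have been confirmed.

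- As the SAP is written: 9/280 = 3.2%.
- If all 20 had angiograms: 14/280 = 5.0%.
- Counting all unreferred severe subjects as failures: (9 + 10)/280 = 6.8%.

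*Adding the category problem.* If 4 further subjects are recorded as >70%, the duplex share at ≥80% is known only to lie between 20/280 = 7.1% and 24/280 = 8.6%. If those 4 have no angiogram and are also counted as failures, the last rate above becomes 23/280 = 8.2%.

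*Numerator subject without a valid duplex.* The denominator wording does not include such a subject. One case changes the rate from 9/281 = 3.20% to 9/280 = 3.21%. This is trivial in size, but it means the rate is not a strict lower bound.

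**The case against.** The strongest reply is that the denominator is deliberate and disclosed. The sentence before it says that angiography is selective, and the SAP revision history records that the restenosis definitions were clarified in June 2014. The obvious alternative, dividing by subjects with an angiogram, would use a group enriched by referral and would be worse. Angiographically confirmed restenosis among duplex-evaluated subjects is a defensible measure. All of this stands, and it is why the endpoint should be kept. But disclosing the selection does not give its size.

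It can also be said that the same section reports the duplex distribution, so severe-duplex counts will appear near the angiographic rate, and that revascularization is reported separately. That is partly right. What is missing is the cross-count with angiogram status, and the distribution is itself unclear above 70%.

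Unseen sources may resolve some of this. The CRF may define >70% or never use it. Protocol 6.4 sends the reader elsewhere for imaging requirements ("Please refer to the Imaging Guidelines for each specific core lab for instructions on submission of images and specific requirements for the images"), and SAP 6.2 places "Title and footnote information" in separate output specifications. None of these was available, so the category point is a request to reconcile and state the rule; it does not show that data were misclassified.

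Several stronger readings are tempting but unsupported:

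- A reader might infer that the overlap spoils the ≥50% ultrasound rate. It does not.
- A reader might take U/N as a ceiling on the whole understatement. It bounds only the severe-duplex part, since a subject in a lower category without an angiogram could also be ≥80% on angiography.
- A reader might take 0.3 to 4.3 points as an estimate. It rests wholly on assumed inputs.
- A reader might treat the sensitivity rate as the corrected value. In the example it is 5 subjects too high, just as the planned rate is 5 too low.

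**Conclusion.** Both parts hold on the printed text, as a minor point about a descriptive secondary endpoint. The duplex categories are not mutually exclusive above 70%, so the distribution cannot be split at 80%. The angiographic ≥80% rate counts a subject with an 80-99% or Occluded duplex and no angiogram as a non-failure, so it is biased low whenever angiography would have confirmed any such subject.

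The size is not derivable from the documents. Each such subject contributes at most 1/N, and the contribution is zero if all are referred. The percentages in the illustrations depend on the assumed N, referral and confirmation fractions and carry no weight in the severity.

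A reader might infer that the device's success criterion is affected. The documents do not support that: the primary endpoint uses neither restenosis measure, and its test, alpha and sample size are untouched.

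**What to change.** **Duplex distribution.** Reconcile the list with the CRF and tabulate exclusive categories: Patent, 50-79%, 80-99%, Occluded. If >70% is a live option, state how it maps. A separate core-lab reading could place such entries, since Protocol 5.4 sends follow-up duplex studies to the ultrasound core lab. However, SAP 4.4 does not say whether the Duplex Scan CRF holds the site or the core-lab reading, so a second reading may not exist. Show entries that cannot be placed in their own row, marked as not classifiable at 80%.

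**Angiographic rate.** Keep the endpoint. Label it angiographically confirmed ≥80% stenosis among duplex-evaluated subjects (minimum estimate). Add numerator subjects to the denominator, as the SAP already does for the MAE rates (4.3, 4.4) and the AE rates (4.5). Beside it report:

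- (a) the number with a follow-up angiogram;
- (b) the number with duplex 80-99% or Occluded and no angiogram;
- (c) a sensitivity rate counting the subjects in (b) as failures, presented as a mixed-modality bracket and not as a corrected estimate.

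If any >70% entries remain unclassifiable, give (b) and (c) with and without them. SAP 4.10 already plans a worst-case analysis for the primary endpoint; (c) applies the same idea to a narrower group.

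**Cost.** SAP wording, one check against the CRF and a few table rows from data already collected. No additional imaging is implied and the protocol endpoint does not change. The downside is a less favourable companion figure that mixes duplex and angiographic readings.
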